#### 6.5.3.3. Duration of Infusion

Study drug will be administered over 2 hours (+ 10 minutes)\*

\*Protocol v5.0: Extended from 1 hour to 1.5 hours due to Grade 3 IRR observed in Cohort 3 (80 mg/m²); effective 20Jul2017 and documented in a study Note to File dated 21Jul2017 (see **Section 2.3.2.1**; AVID100-01: Clinical Experience)

\*Protocol v6.0: Extended from 1.5 hours to 2 hours due to Grade 2 IRRs observed in Cohort 4(120 mg/m2); effective 21Dec2017 and documented in a study Note to File dated 28Dec2017 (see **Section 2.3.2.1**; AVID100-01: Clinical Experience)

Administration should be at a constant rate using a programmable volumetric infusion pump in order to assure accuracy of delivery (as well as integrity of PK sampling). The times of infusion initiation and completion must be recorded on the appropriate page of the patient's eCRF.

Note: In the event of an infusion-related reaction (IRR) that does not meet the protocol definition of DLT, the Investigator may elect to prolong the infusion duration to extend longer than the initially assigned duration (for further instructions see **Section 8.3.1**; Prolongation of Infusion Duration).

During Phase 1a, the duration of infusion will be prolonged for all subsequent patients entered to the trial in the following situations:

- In the event of a Grade 2 IRR in ≥ two thirds of the patients entered to a cohort, the duration of infusion for subsequent patients entered to the trial will be extended by 30 minutes (or longer, if indicated).
- In the event of a Grade 3 or greater IRR in any patient within a cohort, the duration of infusion for subsequent patients entered to the trial will be extended by 30 minutes (or longer, if indicated). Such a case will also be considered to have met the protocol criteria for a DLT, thus requiring expansion of the cohort

These same criteria will be applied in the event IRRs occur on the extended infusion schedule. In such a case, the duration of infusion for subsequent patients entered to the trial will be extended by 30 minutes (or longer, if indicated).

#### 6.5.3.4. Volume of Infusion

All infusions  $\leq 180 \text{ mg/m}^2$  will be delivered in a final volume of 100 mL.

All infusions > 180 mg/m^2 will be delivered in a final volume of 200 to 250 mL. This may include either:

- 100 mL × 2 (dose to be divided between two 100 mL infusion volumes to be administered sequentially).
- Up to 250 mL (using a single flexible IV bag)

#### 6.5.3.5. Diluent

Commercially available sterile 0.9% NaCl for IV infusion is to be used as the diluent.

#### **6.5.3.6.** Schedule

Study drug is to be administered once every 3 weeks (Q3W) on Day 1 of each cycle (3 weeks [21 days] equals 1 dosing cycle).

End of Cycle 1 (EOC1) assessments are to be performed no sooner than C1/D21 (-2 days). Subsequent cycles may be administered Q3W ( $\pm$  2 days), unless further delay is required to allow for amelioration of toxicities.

# 6.6. Cycle 1

A minimum of 1 cycle of AVID100 will be administered, if tolerated. Any interruptions in dosing and the reasons for such interruptions must be documented. If an AE is the cause for dosing interruption, it must be detailed on the Adverse Events page of the eCRF. Determinations regarding cohort escalation, DLTs, and MTD will be based on the toxicities observed during this 3 week period (Cycle 1) of treatment.

- Patients completing Cycle 1, in the absence of a DLT, will be considered to have tolerated the AVID100 regimen.
- Patients must receive their full planned dose of AVID100 during Cycle 1 in order to be considered evaluable for tolerability unless dose reduction, interruption, or discontinuation was the result of a DLT.
- Dose-Escalation Cohorts: Patients will be replaced, if necessary (e.g., received < 1 full dose of AVID100 plus follow-up through EOC1 [C1/D21 {-2 days]}]) for any reason other than a DLT), to allow for a thorough assessment of the tolerability in any dose cohort.

- All enrolled patients will be considered in the assessment of safety and tolerability.

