### 2.6. Justification for the Recommended Phase 2 Dose

The R2PD has been determined to be 220 mg/m² based on observed DLTs at the highest dose level studied,  $270 \text{ mg/m}^2$ . Seven patients were treated at a dose of  $270 \text{ mg/m}^2$  on an every three week (Q3W) schedule. One patient was not evaluable for safety because of the development of brain metastases secondary to primary breast cancer, diagnosed during Cycle 1. Two Grade 3 toxicities were observed at this dose level during Cycle 1 (asymptomatic Grade 3 lipase elevation without evidence of pancreatitis and Grade 4 thrombocytopenia without sequelae). The occurrence of two DLTs in Cycle 1 determined that this dose level exceeded the MTD. Because of this finding, an additional three patients were added to the previous dose level of  $220 \text{ mg/m}^2$ , a dose level that had been tolerated without any  $\geq$  Grade 3 AE that met the DLT criteria in the initial 3 patients evaluated (one patient had experienced Grade 3 elevation of AST but this did not meet the protocol-specified criteria for DLT). No DLTs were observed in Cycle 1 in the additional 3 patients treated at this dose level.

Based on safety and tolerability of the 6 patients evaluated, 220 mg/m^2 was determined to be the MTD and has been selected as the R2PD to be evaluated in three expansion cohorts in patients with metastatic TNBC, SCCHN, and Sq-NSCLC, each with high expression of EGFR as determined by standardized immunohistochemistry (IHC) testing.

Historically, the efficacy of ADCs is dependent upon multiple factors including the relative expression of the target antigen on tumor and normal tissues as well as the delivery of the ADC to the tumor. The latter parameter depends on the delivery of the highest feasible dose given the relatively low proportion of the ADC that is delivered to the tumor. Given the nature of patients enrolled in the Phase 1a segment (refractory to multiple prior therapy and the requirement that they were epithelial tumors potentially responsive to EGFR inhibitors but were not required to overexpress EGFR) a relatively small number of patients were treated on multiple cycles of AVID100. For this reason, it may be necessary to reevaluate the dose utilized in the Phase 2a expansion cohorts based on observed acute and/or longer term tolerability as more experience with the safety and tolerability of AVID100 is obtained.

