# 6.3. **Cohort Management**

For the purposes of this study, "enrollment" is defined as patient registration to participate in this trial; at this time the patient's study identification code and dose cohort will be assigned.

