### 6.6.3.3. Rules for Tolerability in Phase 2a

The criteria for tolerability during Phase 1a will apply to Phase 2a Expansion Cohorts. Safety will be reviewed on an ongoing basis to determine if the dose and schedule chosen based on the Phase 1a dose escalation is safe and well-tolerated in expanded populations of patients with the tumor types selected for the expansion cohorts (mTNBC, SCCHN, and Sq-NSCLC). Should it be determined that the dose is not well-tolerated (i.e.,  $\geq 33.3\%$  of patients in an expansion cohort experience a Cycle 1 DLT), the safety of that dose level will be re-evaluated and the next lower dose with established tolerability in Phase 1a will be administered to subsequent patients.

An exception will be the occurrence of toxicity suggesting organ damage (e.g., pulmonary fibrosis, drug-induced liver injury) occurring in  $\geq 2$  patients within an expanded cohort, in which case further accrual to that cohort will be discontinued.

# 6.7. Continued Therapy After Cycle 1

Upon completion of Cycle 1, in the absence of unacceptable toxicity or disease progression, patients may continue receive additional cycles of study drug Q3W ( $\pm$  2 days), unless further delay is required to allow for amelioration of toxicities. Administration of subsequent dosing cycles is allowable at the discretion of the Investigator, provided the patient meets the retreatment criteria listed below. Additional cycles should be initiated as soon as possible, but not longer than 2 weeks after the completion of the previous cycle, if feasible.

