# 6.9. **Definition of Maximum Tolerated Dose**

The clinical endpoint of the Phase 1a portion of this trial is determination of the MTD of study drug that can be administered by the specified route, infusion duration, and schedule.

MTD will be defined as the dose below that which produces, during Cycle 1 of treatment, any of the indicated DLTs either in > 1 patient in a 3 to 6 patient cohort, or in  $\ge 33.3\%$ \* of patients in the event of an expanded 7 to 12 patient cohort.

\*i.e., > 2 DLTs when 7 to 9 patients have been treated.

The MTD will not be established until all patients entered into the cohort under evaluation have either completed Cycle 1 or discontinued further participation in the trial (or been dose-reduced) due to the occurrence of a DLT.

Previously established tolerability of a dose level will be reevaluated if DLTs thought to be possibly related, probably related, or related to study drug are observed in later cycles.

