## 9.2. **Replacements**

Phase 1a: Dose-Escalation: Should a patient discontinue treatment with study drug for reasons other than the occurrence of a study drug-induced toxicity prior to completing Cycle 1 a replacement patient will be obtained using the original eligibility criteria. Patients discontinued due to study drug-associated toxicity will not be replaced.

Note: Patients must receive their full planned dose of AVID100 during Cycle 1 in order to be considered evaluable for tolerability, unless dose reduction, interruption, or discontinuation is the result of a DLT. Patients receiving < 1 full planned study drug dose plus 3 weeks of follow-up during Cycle 1 for reasons other than toxicity will be replaced.

Phase 2a Dose-Expansion: It is not planned to replace any patients in the 3 dose-expansion cohorts.

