### 14.3.1 Analysis Sets

- Safety analyses will be conducted on patients receiving any amount of a AVID100 dose (partial or complete). Patients completing Cycle 1 in the absence of a DLT, will be considered to have tolerated the AVID100 regimen. Patients must receive their planned dose of AVID100 during Cycle 1 plus 2 weeks of follow-up in order to be considered evaluable for tolerability, unless dose reduction, interruption, or discontinuation was the result of a DLT.
- PK analyses will be performed in Dose Escalation Cohorts and Expansion Cohorts on patients who receive any amount of their assigned dose of AVID100 and have an adequate number of concentration determinations to allow for PK calculation.
- All enrolled\* patients will be evaluated for antineoplastic activity. In addition, patients who complete Cycle 2 (6 weeks) of treatment, receive at least 2 planned doses during that period, and have a follow-up assessment of disease status will be considered evaluable for assessment of antineoplastic activity. Patients who are withdrawn from the study before completion of Cycle 2 because of progressive disease also will be included in assessments of antineoplastic activity.

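### The Cycle 1 DLT rate has no single denominator: the protocol counts evaluable patients in one rule and all enrolled patients in another, and the Phase 2a 33.3% trigger does not say which applies

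*Combined protocol and SAP*

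**What the plan says.** **Who counts.** Section 6.6 states: "Patients must receive their full planned dose of AVID100 during Cycle 1 in order to be considered evaluable for tolerability", except where a DLT caused the shortfall. Two bullets later it states: "All enrolled patients will be considered in the assessment of safety and tolerability". The synopsis repeats both rules. Section 6.3 says that enrollment "is defined as patient registration to participate in this trial", which comes before any dose. The replacement bullet between the two rules is limited to the dose-escalation cohorts; the two rules themselves are not.

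**Follow-up needed.** Section 9.2 asks for 3 weeks after the Cycle 1 dose. Section 14.3.1 says: "Patients must receive their planned dose of AVID100 during Cycle 1 plus 2 weeks of follow-up in order to be considered evaluable for tolerability".

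**The Phase 2a trigger.** Section 6.6.3.3 and the synopsis act when at least 33.3% "of patients in an expansion cohort experience a Cycle 1 DLT". Section 3.3 puts the same rule at 33% or more of the patients entered. On replacement, Section 9.2 says: "It is not planned to replace any patients in the 3 dose-expansion cohorts".

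**The one worked case.** Section 2.6 reports seven patients treated at 270 mg/m² and adds: "One patient was not evaluable for safety because of the development of brain metastases secondary to primary breast cancer, diagnosed during Cycle 1". Two patients had Cycle 1 DLTs, and the dose was judged to exceed the MTD. Section 6.9 sets the limit at more than 1 patient with a DLT in a cohort of 3 to 6, and at 33.3% or more in an expanded cohort of 7 to 12 ("i.e., > 2 DLTs when 7 to 9 patients have been treated"). Section 6.6.2.2.1 stops escalation once more than 1 patient has a DLT and names no denominator.

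**The concern.** The two bullets in Section 6.6 attach different populations to the same word, tolerability. In Phase 1a, replacement largely removes the difference, because each cohort is filled with evaluable patients. In Phase 2a nobody is replaced and the rule is a percentage, so the choice of denominator can change the answer.

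The difference runs one way. A patient with a Cycle 1 DLT is counted under both rules. A patient who is not evaluable adds to the all-enrolled denominator and nothing to the numerator. The all-enrolled rate therefore cannot exceed the evaluable rate. (This reads the exception in Section 6.6 as keeping every patient with a Cycle 1 DLT; its literal words cover those whose dosing shortfall the DLT caused.)

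The trigger decides whether the dose given to later patients is reconsidered. Two people applying the protocol to identical data could reach opposite answers.

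**Working it through.** **Inputs.** Threshold of one third (Section 6.6.3.3). Cohorts of 15, and 30 for mTNBC (Section 14.2). At 270 mg/m²: 7 treated, 1 non-evaluable, 2 DLTs (Section 2.6). The documents give neither a Phase 2a DLT rate nor a non-evaluable rate, so both are assumed over ranges.

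**1. Reproduce the plan's own limits.** The smallest count k with k/n ≥ 1/3 is n/3 rounded up. For n = 7 to 9 this is 3, and for n = 10 to 12 it is 4. These match the footnotes in Sections 6.9 and 6.6.2.2.1. At 270 mg/m², 2 of 6 evaluable patients is more than 1 in a cohort of 3 to 6, so the stated call is reproduced.

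**2. The 270 mg/m² case on both denominators.** Evaluable: 2/6 = 33.3%. All treated: 2/7 = 28.6%, below the 3 DLTs that Section 6.9 needs at n = 7 if those seven are an expanded cohort. Under Section 6.6.2.2.1, two patients with DLTs exceed the MTD whether 6 or 7 are counted.

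**3. Phase 2a trigger at full size.**
- 15 enrolled: 15/3 = 5 DLTs on the all-enrolled denominator. On the evaluable denominator, 5 with 0 to 2 non-evaluable patients and 4 with 3 to 5. For example, 4 DLTs with 3 non-evaluable are 4/12 = 33.3% (met) or 4/15 = 26.7% (not met).
- 30 enrolled: 10 on all enrolled. On evaluable patients, 10 with up to 2 non-evaluable, 9 with 3 to 5, and 8 with 6.
- Writing 33% instead of 33.3% changes nothing here: the largest fraction below one third with n up to 30 is 9/28 = 32.1%.

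**4. Trigger at running counts.** Section 6.6.3.3 calls for ongoing review. One non-evaluable patient changes the required count at 7 enrolled (3 to 2), at 10 (4 to 3) and at 13 (5 to 4).

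**5. Chance of triggering with 15 enrolled.** Let m be the number evaluable and X ~ Binomial(m, true DLT rate). The all-enrolled reading needs X ≥ 5. The evaluable reading needs X ≥ m/3 rounded up. Each cell gives all-enrolled / evaluable, for a single look at full size.

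| Non-evaluable (m) | 25% | 33.3% | 40% | 50% |
|---|---|---|---|---|
| 1 (14) | 25.8 / 25.8 | 52.4 / 52.4 | 72.1 / 72.1 | 91.0 / 91.0 |
| 2 (13) | 20.6 / 20.6 | 44.8 / 44.8 | 64.7 / 64.7 | 86.7 / 86.7 |
| 3 (12) | 15.8 / 35.1 | 36.8 / 60.7 | 56.2 / 77.5 | 80.6 / 92.7 |
| 4 (11) | 11.5 / 28.7 | 28.9 / 52.7 | 46.7 / 70.4 | 72.6 / 88.7 |
| 5 (10) | 7.8 / 22.4 | 21.3 / 44.1 | 36.7 / 61.8 | 62.3 / 82.8 |

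With 30 enrolled and a true rate of 40%, the figures are 69.1% / 81.6% with 3 non-evaluable and 51.1% / 80.8% with 6.

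**The case against.** The strongest reply is that the protocol can be read coherently: safety on everyone, tolerability on evaluable patients, with the specific bullet governing the general one. Section 6.6.3.3 also opens by carrying the Phase 1a tolerability criteria into Phase 2a, and Section 2.6 shows the sponsor setting aside a non-evaluable patient. This points to the probable intent but does not settle the text. The synopsis uses safety and tolerability together for both rules, the criteria carried over contain the same conflict, and Section 3.3 counts patients entered. Appendix F adds a third population by making all patients evaluable for toxicity from first treatment.

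A reader might infer three stronger things that the documents do not support.
- **That the denominator decided the 270 mg/m² call.** It did not. The stop rule in Section 6.6.2.2.1 gives the same answer with 6 or 7 patients. The 7 to 12 clause in Section 6.9 is written for an expanded cohort, and Section 4.1.2 lets a cohort of 6 become 7 simply to secure evaluable patients.
- **That non-evaluable patients could not have shown a DLT.** This is true only of patients registered and never dosed. Partly dosed or early-exit patients can have one, and failure to complete Cycle 1 because of Grade 3 or worse toxicity is itself a DLT (Section 6.8.3).
- **That the 33.3% rule is the only numeric protection in Phase 2a.** Section 6.6.3.3 also closes accrual to a cohort when toxicity suggesting organ damage occurs in 2 or more patients. That rule is a count and cannot be diluted.

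It is also fair that 3 non-evaluable of 15 is the smallest number that moves the full-size trigger.

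**Conclusion.** The concern holds as an unresolved conflict over the denominator of a decision rule. Followed literally, the all-enrolled wording can only lower the observed Cycle 1 DLT rate, and Phase 2a has no replacement to offset this. In a cohort of 15 with 3 non-evaluable patients, the chance of triggering differs by 12 to 24 percentage points over true DLT rates of 25% to 50% (80.6% against 92.7% at 50%; 36.8% against 60.7% at 33.3%). With 1 or 2 non-evaluable there is no difference at full size, though one such patient matters at running counts of 7, 10 or 13.

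These sizes rest on assumed non-evaluable numbers and DLT rates, and on a single look. The 270 mg/m² call stands. That case shows only that the sponsor's practice departed from the all-enrolled bullet, and that Sections 6.9 and 6.6.2.2.1 could disagree if all seven treated patients were counted as an expanded cohort.

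**What to change.** Reconcile the synopsis (Cycle 1 and the Phase 2a tolerability rules) with Sections 3.3, 6.6, 6.6.3.3, 6.9, 9.2 and 14.3.1, so that all of them use one stated denominator and one follow-up window for the Cycle 1 DLT rate. State explicitly that any patient with a Cycle 1 DLT is counted. In Section 6.9, say which patients the 7 to 12 clause counts and how it fits with the stop rule in Section 6.6.2.2.1. The evaluability definition already in Section 6.6 is the one that avoids dilution. Adverse event summaries should stay on all treated patients. Thresholds and doses are for the sponsor and are not addressed here.

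The cost is wording in a handful of places, with no added patients or procedures. The choice does have a statistical price. On the evaluable denominator the trigger is met more often, including at true rates within the protocol's own target of 33.3% or less: from 15.8% to 35.1% at a true rate of 25% in the example with 3 of 15 non-evaluable.

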#### 6.6.1 Premedication

#### 6.6.1.1. Premedication for Infusion-Related Reactions

Beginning with the first dose, all patients must be premedicated with standard therapies prior to each dose of AVID100 to reduce the risk of IRRs associated with study drug.

The recommended premedication regimen includes administration of dexamethasone 12 hours and 6 hours prior to each dose, as well as administration to begin at minimum 30 minutes prior to each infusion of a glucocorticoid (e.g., dexamethasone) as well as an H1 (e.g., diphenhydramine/hydroxyzine) and an H2-blocker (e.g., ranitidine/famotidine) (see **Section 8.2**; Premedication for Study Drug-Related Toxicities).

#### 6.6.1.2. Use of Other Premedications

In the event of other study-drug associated reactions (e.g., nausea, vomiting, diarrhea, etc.), patients may be premedicated with standard therapies in order to reduce the potential for such reactions in the future.

Mandatory premedication will be implemented for all patients should a pattern begin to emerge of mild-to-moderate study drug-related reactions that are amenable to prophylaxis with standard agents.

#### 6.6.2 Phase 1a: Rules for Accrual

### 6.6.2.1. Filling of Cohorts in Phase 1a

Cohorts will be filled sequentially during the Phase 1a dose escalation portion of the study. Once assigned to a cohort, each patient will continue to be treated at the same dose level and schedule of study drug throughout the course of the study (unless dose reduction is necessary due to the occurrence of a DLT).

#### 6.6.2.2. Rules for Dose Escalation and Cohort Expansion in Phase 1a

Dose escalation of AVID100 is based on demonstrated tolerability during Cycle 1 (i.e., the initial 3 weeks of dosing) and the occurrence of DLTs\* thought to be associated with (i.e., possibly related, probably related, or related to) study drug. The rules for dose escalation and identification of the MTD(s)\* in this study are as follows:

\*See Section 6.8.3; Definition of DLT and Section 6.9; Definition of Maximum Tolerated Dose

#### 6.6.2.2.1. Establishment of the MTD

- 1. Dose Part A: A minimum of 1 patient will be entered into dose Cohort 1 and 2 ONLY; the dose escalation between cohorts (until at most Cohort 3) will be 100%.
  - If during Cycle 1, a patient experiences a ≥ Grade 2 toxicity considered associated with study drug, the cohort will be expanded to 3 patients and Part B will commence.

- If during Cycle 1, a patient experiences a DLT considered associated with study drug, the cohort will be expanded to 6 patients and Part C will commence.
- 2. Dose Part B: A minimum of 3 patients will be entered into each dose cohort; the dose escalation between cohorts will be 50%.
  - If during Cycle 1, any 1 patient experiences a DLT considered associated with study drug, the cohort will be expanded to 6 patients and Part C will commence.
  - If during Cycle 1, > 1 patient experiences a DLT, dose escalation will STOP. This will indicate that the MTD has been exceeded.
- 3. Dose Part C: A minimum of 6 patients will be entered into any dose cohort where a DLT is observed in any of the first 3 patients, otherwise a minimum of 3 patients will be entered into each dose cohort; the dose escalation between cohorts will be 25%.
  - If during Cycle 1, > 1 patient experiences a DLT, dose escalation will STOP. This will indicate that the MTD has been exceeded.
- 4. If it is determined that a dose level is not tolerated, the previous lower dose cohort will be expanded to 6 patients (if this has not already been accomplished) as a total of 6 patients must be treated before establishing a dose as the MTD.
- 5. Once the MTD (or maximum dose to be studied) is achieved and the RP2D is identified, that cohort may be expanded up to 12 patients in order to more fully evaluate safety and tolerability at that dose level at the Sponsor's discretion.
- 6. Should the DLT rate equal or exceed 33.3%\* in an expanded MTD cohort, it will be determined that the dose is not tolerated. If this occurs, the previous lower dose cohort may be expanded as above. Therefore:
  - There is potential for expansion of lower dose cohort(s) if the initially identified MTD is not tolerated (either with single or repeat cycles of therapy), and
  - There is potential to evaluate and expand a previously unexamined intermediate dose level(s) between 2 established dose levels in order to more fully characterize tolerability.

Note: Such action would be taken by the Sponsor (or designee) in the event of an unacceptably high frequency of toxicities observed in patients treated at one dose level, considered to be in marked contrast to the tolerability noted in the immediately preceding dose cohort.

\*i.e., > 2 DLTs when 7 to 9 patients have been treated, > 3 DLTs when 10 to 12 patients have been treated, etc.

Note: Based on emerging tolerability data the Sponsor may choose to escalate the dose between cohorts at an increment less than the percent increase allowed above in an effort to protect patient safety.

